Listing 3 Prohibited Live/Live Attenuated Vaccines Within 3 Months Before Randomization Until the Last Treatment Visit (this does not apply to non-live/inactivated vaccines)

Bacterial vaccines	Viral vaccines
Bacillus Calmette-Guérin vaccine against tuberculosis	Measles vaccination
Typhoid vaccination (oral)	Mumps vaccination
Cholera vaccination (oral)	Rubella vaccination
	Oral polio vaccination (Sabin)
	Yellow fever vaccination
	Varicella (chickenpox) vaccination
	Rotavirus vaccination
	Japanese encephalitis vaccination
	Live attenuated influenza vaccine (FluMist in the United States and Canada, and Fluenz in Europe)

This list is not exhaustive

Permitted Prior/Concomitant Medications

Listing 4 Medications Which Need To Be on a Stable Dose for 12 Weeks Before the Cognitive Assessments at Visit 2 and Should Remain on the Same Stable Dose From Visit 2 to Follow Up Visit 15

Cognitive Enhancers	
Donepezil	Aricept
Rivastigmine	Exelon
Galantamine	Reminyl
Memantine	Namenda

Listing 5 Permitted Medications Used on PRN Basis Which are not to be Used Within 72 Hours Before Cognitive Testing

Generic name	Trade name
Opiates	
Morphine	Astramorph PF, Avinza, Depo Dur, Duramorph, Infumorph, Kadian, MS Contin, MSIR, Oramorph SR, RMS, Roxanol
Opiate Agonists	
Meperidine	Demerol, Meperitab
Fentanyl	Actiq, Duragesic, Fentora, Onsolis, Sublimaze
Codeine	Codeine
Oxycodone	Dazidox, Endocodone, Eth-OxyDose, OxyContin, OxyFast, OxyIR, Percolone, Roxicodone, Roxicodone Intensol
Other opioids or opioid agonists which are used on PRN basis	
Benzodiazepines and sedatives	
Estazolam	ProSom
Alprazolam	Alprazolam Intensol, Niravam, Xanax
Triazolam	Halcion
Midazolam	Versed
Lorazepam	Ativan
Flunitrazepam	Rohypnol
Temazepam	Restoril
Clonazepam	Ceberclon, Klonopin
Diazepam	Diastat, Dizac, Valium
Chlordiazepoxide	H-Tran, Librium
Flurazepam	Dalmane
Zopiclone	(various)
Zolpidem	Ambien; others
Ramelteon	Rozerem
Amitriptyline	(various)
Dothiepin	(various)
Risperidone	Risperdal
Olanzapine	Zyprexa
Promethazine	Phenergan; others
Other benzodiazepines, tricyclic antidepressants, antipsychotics and other drugs which are used on PRN basis as sedatives	

PRN = Pro re nata

This list is not exhaustive

Listing 6 Permitted Medications

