increase (by approximately 70%) of the area under the concentration x time curve (AUC) of E2609. Rifampin (a potent CYP3A4 inducer) caused a mild decrease (by approximately 20%) of the AUC of E2609. Donepezil (a moderate CES2 inhibitor) caused a mild increase (by approximately 20%) of the AUC of E2609 when coadministered with E2609 but not when dosed at least 2 hours apart from E2609. E2609 (which inhibits the P-glycoprotein 1 transporter) did not affect the PK properties of digoxin. Nonclinical studies also indicated that other CYP pathways apart from CYP3A4 would not be major pathways of metabolism of E2609. Based on these results, it is not considered necessary to impose restrictions during E2609 treatment on the use of concomitant medications that may be CYP3A4 inhibitors or other CYP enzymes inhibitors. Similarly, it was also not considered necessary to restrict the use of concomitant medications which are inducers of CYP450 enzymes. Given the results of study 003 moderate to strong CES2 enzyme inhibitors are not permitted for a period of 5 half-lives or 7 days (whichever is longer) before randomization and until the last treatment visit.

However, simvastatin use is permitted only with once daily evening administration. Simvastatin use is recommended with night time administration as physiological studies showed that most cholesterol is synthesized when dietary intake is at its lowest. It is therefore expected that the PK interaction between E2609 and simvastatin is minimized because simvastatin is thought to mainly inhibit CES2 in the intestine when E2609 will not be present as it will be administered in the morning.

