 - b. CDR global score of 0.5
 - c. CDR Memory Box score of 0.5 or greater
2. A history of subjective memory decline with gradual onset and slow progression over the last 1 year before Screening; this MUST be corroborated by a study partner
3. Cognitive impairment of at least 1 SD from age-adjusted norms in total recall or delayed recall on the ISLT.
4. Positive biomarker for brain amyloid pathology as indicated by at least 1 of the following:
 - a. PET assessment of amyloid imaging agent uptake into brain. Note: amyloid PET screens will be performed according to local regulatory guidelines and thus may be restricted for those subjects who are not suitable for lumbar puncture (LP) to obtain CSF for testing of eligibility.
 - b. CSF AD assessment(eg, tau:Aβ(1-42) ratio) (revised per Amendment 03)

NOTE: Subjects may undergo both the amyloid PET and CSF assessments, but need a positive amyloid result in only 1 of the 2 procedures to confirm eligibility. Subjects who consent to amyloid PET or CSF for eligibility purposes are not required to participate in the amyloid PET or CSF longitudinal substudies. Use of a historical amyloid positive PET (conducted within 12 months before the planned date of randomization) is acceptable for determination of eligibility but will not suffice for the baseline assessment if the subject wishes to consent to the amyloid PET longitudinal substudy. The historical imaging data must be made available to the sponsor. Historical CSF samples, if collected, processed, and stored under appropriate conditions and approved by the sponsor, may be analyzed to determine CSF amyloid positivity. (revised per Amendments 03 and 05).
5. Male or female subjects between 50 and 85 years of age, inclusive at the time of consent
6. If receiving an acetylcholinesterase inhibitor (AChEI) or memantine or both for AD, must be on a

stable dose for at least 12 weeks before Randomization. Treatment-naïve subjects with AD can be entered into the study.

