15. Malignant neoplasms within 5 years of Screening (except for basal or squamous cell carcinoma in situ of the skin, or localized prostate cancer in male subjects with treatment cycles completed at least 6 months before Screening). Subjects who had malignant neoplasms but who have had at least 5 years of documented uninterrupted remission before Screening need not be excluded.
16. Hypopigmentation conditions (eg, albinism and vitiligo). Hypopigmentation associated with scarring need not be exclusionary
17. Known or suspected history of drug or alcohol abuse or dependence within 2 years before Screening
18. Taking prohibited medications
19. Have participated in a clinical study involving:
- any therapeutic monoclonal antibody, protein derived from a monoclonal antibody, immunoglobulin therapy, or vaccine within 6 months before Screening for whom it cannot be documented that they were randomized only to placebo or never received study drug
 - elenbecestat
 - any new chemical entity or investigational drug for AD with last study drug dose occurring within 6 months before Screening unless it can be documented that the subject received only placebo (revised per Amendment 05)
 - any other investigational medication (unless it can be documented that the subject received only placebo) or device within 8 weeks or 5 half-lives (whichever is longer) before

randomization
20. Planned surgery that requires general, spinal, or epidural anesthesia that would take place during the study. Planned surgery which requires only local anesthesia and which can be undertaken as day case without inpatient stay postoperatively need not result in exclusion if in the opinion of the investigator this operation does not interfere with study procedures and subject safety.
Study Treatments
Core Study Elenbecestat will be supplied by the sponsor as tablets of 50-mg dose strength in bottles of 35 tablets each. Placebo tablets to match elenbecestat will be of identical appearance. Each subject will receive 1 tablet of 50 mg elenbecestat or an identical placebo tablet, to be administered orally QD in the morning with or without food.
Extension Phase Elenbecestat will be supplied by the sponsor as tablets of 50-mg dose strength in bottles of 35 tablets. Each subject will receive 1 tablet of 50 mg elenbecestat, to be administered orally QD in the morning with or without food. (revised per Amendment 05)
Duration of Treatment

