Core Study: The maximum estimated duration for each subject is approximately 29 months (ie, 2-month Prerandomization Phase, followed by 24 months of blinded treatment in the Randomization Phase and a 3-month follow-up). Extension Phase: The estimated duration for a subject is 25 months (ie, 24 months of treatment and 1-month follow-up. (revised per Amendment 05).
Concomitant Drug/Therapy (both Core Study and Extension Phase) The following agents are not permitted before randomization (specific time frames are shown below) and until the last visit during the Treatment Period: (revised per Amendment 01) 
a) Immunoglobulin therapy and biologic drugs are not permitted within 6 months before Screening and until the last visit during the Treatment Period (revised per Amendment 01)b) Systemic immunosuppressive or immunomodulatory drugs are not permitted for a period of 5 half-lives or 60 days (whichever is longer) before randomization and until the last visit during the Treatment Period (revised per Amendments 01 and 03)c) Moderate to strong inhibitors of carboxylesterase 2 (CES2) enzyme activity are not permitted for a period of 5 half-lives or 7 days (whichever is longer) before randomization and until the last treatment visit. Simvastatin use is permitted only with QD evening administration.d) Live/live attenuated vaccines are not permitted within 3 months before randomization and until the last treatment visit (this does not apply to non-live/inactivated vaccines) (revised per Amendment 01) 
Concomitant therapy with AChEI or memantine should only be allowed and/or acceptable for the region or country in which the study is being conducted and should follow the local standard of care for symptomatic treatment (revised per Amendment 01). Subjects who are taking AChEI or memantine will be required to be on a stable dose for at least 12 weeks before randomization. Initiation or termination of therapy or changing dose of AChEIs or memantine during the study should be undertaken in compliance with local standard of care for symptomatic treatment of AD. (revised per Amendments 02 and 05) Subjects who start on AChEI or memantine or change their

dose during the Treatment Period will be permitted to continue in the study; however, subjects should not undertake cognitive assessments until they have been on a stable dose for at least 4 weeks.

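### Donepezil falls inside the protocol's prohibited CES2-inhibitor class by the protocol's own description, yet is named as permitted, and no sentence shown reconciles the two

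*Protocol*

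**What the plan says.** **The ban.** Item c of Concomitant Drug/Therapy in the Version 7.0 synopsis reads "Moderate to strong inhibitors of carboxylesterase 2 (CES2) enzyme activity are not permitted for a period of 5 half-lives or 7 days", taking the longer period, and continues the restriction to the last treatment visit. Exclusion criterion 18 ("Taking prohibited medications") turns it into an entry rule. The only exception written into item c is simvastatin, allowed with once-daily evening dosing.

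**The classification.** Section 7.1 of the original protocol version reports Study 003: "Donepezil (a moderate CES2 inhibitor) caused a mild increase (by approximately 20%) of the AUC of E2609 when coadministered with E2609". It then limits that finding with the words "but not when dosed at least 2 hours apart from E2609". Shortly afterwards it draws the rule: "Given the results of study 003 moderate to strong CES2 enzyme inhibitors are not permitted".

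**The permission.** Inclusion criterion 6 begins "If receiving an acetylcholinesterase inhibitor (AChEI) or memantine or both for AD" and admits such subjects on a stable dose. The paragraph that follows the prohibited list in the synopsis says the same: "Subjects who are taking AChEI or memantine will be required to be on a stable dose for at least 12 weeks before randomization". Appendix 2, Listing 4, headed "Medications Which Need To Be on a Stable Dose for 12 Weeks Before the Cognitive Assessments at Visit 2", names donepezil among the permitted cognitive enhancers. Listing 1, the prohibited CES2 inhibitors, does not name it. Concurrent AD medication use is a randomisation stratum and a term in the primary model.

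**The PK analysis.** The Version 7.0 synopsis plans a population PK model and gives its covariates as demographics, introduced by ie rather than eg.

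**The concern.** A class rule and a named permission give opposite answers for the same subject. Item c is written by class, and on the protocol's own description donepezil belongs to that class, so a monitor working from item c and Section 7.1 could call a donepezil user ineligible. A monitor working from Listing 4 would call the same subject eligible. The conflict continues after randomisation. Version 7.0 lets subjects start, stop or change AChEIs under local standard of care, while item c bans the class until the last treatment visit.

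The second issue is exposure. Section 7.1 shows that the interaction depends on the interval between doses. For simvastatin, the protocol turned a timing argument into a dosing condition. For donepezil, it reports direct timing evidence, and nothing shown carries that evidence into an instruction, an explicit statement that none is needed, or a PK covariate. What is at stake is consistent deviation classification and per-protocol membership, and the quality of the population PK secondary objective.

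**Working it through.** **Side-by-side reading**

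| Source | Effect on donepezil |
|---|---|
| Section 7.1 (original version) | A moderate CES2 inhibitor |
| Synopsis item c (original version and Version 7.0) | Moderate to strong CES2 inhibitors banned, as a class |
| Exclusion 18 | Use of a prohibited drug excludes |
| Listing 1 (versions shown) | Not named |
| Appendix 2 introduction | Listings may be incomplete |
| Inclusion 6 | AChEI users admitted if stable for 12 weeks |
| Listing 4 (versions shown) | Named as permitted |

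The first three rows prohibit donepezil and the last two permit it. Absence from Listing 1 does not settle the matter, because item c does not confine the ban to the listed drugs.

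**Version check.** Item c, exclusion 18 and inclusion 6 are quoted from Version 7.0. Its Sections 7.1 and 9.4.7 and Appendix 2 are not shown. The conflict does not depend on mixing versions, because the original version contains every element: the classification in 7.1, the ban in 9.4.7, inclusion 6, and Listings 1 and 4. The revision history up to Version 7.0 records itraconazole being added to Listing 1, and footnotes to Listing 4 on starting, stopping or changing dose and on herbal products. It records no donepezil exemption or timing condition.

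**Size of the exposure difference**

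Inputs: AUC ratio 1.20 when taken together and 1.00 when at least 2 hours apart (Section 7.1). Let f be the share of a group of active-arm subjects who take donepezil close to study drug. The documents do not give f, so a range is assumed.

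Mean AUC ratio for the group = f × 1.20 + (1 − f) × 1.00 = 1 + 0.20f

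| f (assumed) | Mean AUC ratio |
|---|---|
| 0.10 | 1.02 |
| 0.25 | 1.05 |
| 0.50 | 1.10 |
| 1.00 | 1.20 |

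For an individual, if exposure is dose-proportional, 50 mg × 1.20 = 60 mg: about the exposure of a 60 mg dose. The last row is a bound, not an expectation. It needs every subject in the group to take donepezil close to the morning dose, whereas the AD-medication stratum also holds users of rivastigmine, galantamine and memantine.

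**Effect on the treatment comparison.** Randomisation is stratified by concurrent AD medication, so use at entry is balanced between arms in expectation. The interaction acts on study-drug exposure and therefore only within the active arm. It could slightly modify an effect, but it cannot create a spurious difference between arms. No sample-size, power or alpha figure is involved.

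**The case against.** The strongest reply is that no site would be in doubt. Listing 4 names donepezil, Listing 1 does not, the AChEI paragraph follows item c closely, and a named permission normally overrides a class rule. The caveat about incomplete listings refers investigators to the medical monitor for drugs that are not listed, and donepezil is listed. Most of this stands. A reader might infer that donepezil users would be screened out. The documents do not support that, because Listing 4 is explicit and sites would almost certainly follow it. What remains is that no sentence shown says Listing 4 prevails, so an auditor could still reach the other answer.

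A reader might also infer that safety comparisons by prior AChEI use are confounded. They are not: adverse-event summaries within those subgroups compare randomised arms. Nor do the documents say that donepezil alone prompted the ban. Section 7.1 attributes it to Study 003 as a whole, which includes itraconazole at about 70% higher AUC, and calls donepezil's effect mild.

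Exposure is also measured. Individual AUC comes from posterior clearance, with predose and postdose samples at seven visits, so exposure-response does not assume equal exposure across strata. That is fair, but a systematic donepezil effect left out of the model would be absorbed into unexplained between-subject variability.

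Finally, covariate lists are often left to a later analysis plan. Silence here would be no finding. The protocol is not silent, because it gives the covariates as demographics.

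**Conclusion.** The point holds as a conflict between rules with modest consequences. It is complete within the original protocol version, and neither the Version 7.0 synopsis nor the revision history shows it resolved. Whether the unseen Version 7.0 body resolves it cannot be checked.

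The likely harm is inconsistent eligibility and deviation classification, and a mild exposure difference within the active arm for which the named PK covariates do not account. That difference is 0.2f. It rests on the protocol's own 20% figure and on an unknown f. The randomised treatment comparison is not confounded, and the primary result is unlikely to move. The point is worth correcting because the correction is almost free.

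**What to change.** 1. Reconcile item c, exclusion 18, inclusion 6, Listing 1, Listing 4 and the Section 7.1 classification, so that donepezil's status is stated once and the same way throughout. Whether it is exempt, exempt with a condition, or prohibited is a clinical pharmacology decision for the sponsor. This review does not propose an answer.
2. Extend the population PK covariates beyond demographics to include donepezil co-medication, treated as time-varying because AChEI use may change during the study. The data already exist, since concomitant medication is recorded in the eCRF.
3. Optionally, record donepezil intake time at the telephone contact before PK sampling, which already documents the study-drug time. Without it, the covariate estimates an average over subjects who do and do not take the two drugs close together.

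The cost is amendment wording and one additional model covariate. The optional step adds one recorded time per contact. Sample size, visit schedule and primary analysis are unchanged.
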